**Table 4 Aspirin Dose Modification Guidelines for Drug-Related Adverse Events**

Toxicity	Hold Treatment For Grade	Timing for Restarting Treatment	Treatment Discontinuation
GI Bleeding	2	Toxicity resolves to Grade 0-1	Toxicity does not resolve within 2 weeks, or continued bleeding, or life threatening or serious Grade 3 or 4 hemorrhage
	3-4	Permanently discontinue	Permanently discontinue
Renal Failure or Nephritis	2	Toxicity resolves to Grade 0-1	Toxicity does not resolve within 4 weeks
GI Ulceration	1-2	Use omeprazole or PPI or sucralfate if not currently being used	May continue aspirin if symptoms resolve with treatment
	3-4 or Severe	Toxicity resolves to Grade 1 or 0	Life threatening or serious Grade 3 or 4 toxicity

## 5.4 Rescue Medications & Supportive Care

### 5.4.1 Supportive Care Guidelines

Subjects should receive appropriate supportive care measures as deemed necessary by the treating investigator. Suggested supportive care measures for the management of adverse events with potential immunologic etiology are outlined below. Where appropriate, these guidelines include the use of oral or intravenous treatment with corticosteroids as well as additional anti-inflammatory agents if symptoms do not improve with administration of corticosteroids. Note that several courses of steroid tapering may be necessary as symptoms may worsen when the steroid dose is decreased. For each disorder, attempts should be made to rule out other causes such as metastatic disease or bacterial or viral infection, which might require additional supportive care. The treatment guidelines are intended to be applied when the investigator determines the events to be related to pembrolizumab.

Note: if after the evaluation the event is determined not to be related, the investigator does not need to follow the treatment guidance (as outlined below). Refer to Section 5.3 for dose modification.

It may be necessary to perform conditional procedures such as bronchoscopy, endoscopy, or skin photography as part of evaluation of the event.

- **Pneumonitis:**
  - For **Grade 2 events**, treat with systemic corticosteroids. When symptoms improve to Grade 1 or less, steroid taper should be started and continued over no less than 4 weeks.
  - For **Grade 3-4 events**, immediately treat with intravenous steroids. Administer additional anti-inflammatory measures, as needed.
  - Add prophylactic antibiotics for opportunistic infections in the case of prolonged steroid administration.
- **Diarrhea/Colitis:** Subjects should be carefully monitored for signs and symptoms of enterocolitis (such as diarrhea, abdominal pain, blood or mucus in stool, with or without fever) and of bowel perforation (such as peritoneal signs and ileus).
  - All subjects who experience diarrhea/colitis should be advised to drink liberal quantities of clear fluids. If sufficient oral fluid intake is not feasible, fluid and electrolytes should be substituted via IV infusion. For Grade 2 or higher diarrhea, consider GI consultation and endoscopy to confirm or rule out colitis.
  - For **Grade 2 diarrhea/colitis**, administer oral corticosteroids.
  - For **Grade 3 or 4 diarrhea/colitis**, treat with intravenous steroids followed by high dose oral steroids.
  - When symptoms improve to Grade 1 or less, steroid taper should be started and continued over no less than 4 weeks.
- **Type 1 diabetes mellitus (if new onset, including diabetic ketoacidosis [DKA]) or ≥ Grade 3 Hyperglycemia, if associated with ketosis (ketonuria) or metabolic acidosis (DKA)**
  - For **T1DM or Grade 3-4 Hyperglycemia**
    - Insulin replacement therapy is recommended for Type I diabetes mellitus and for Grade 3-4 hyperglycemia associated with metabolic acidosis or ketonuria.
    - Evaluate patients with serum glucose and a metabolic panel, urine ketones, glycosylated hemoglobin, and C-peptide.
- **Hypophysitis:**
  - For **Grade 2 events**, treat with corticosteroids. When symptoms improve to Grade 1 or less, steroid taper should be started and continued over no less than 4 weeks. Replacement of appropriate hormones may be required as the steroid dose is tapered.
  - For **Grade 3-4 events**, treat with an initial dose of IV corticosteroids followed by oral corticosteroids. When symptoms improve to Grade 1 or less, steroid taper should be started and continued over no less than 4 weeks. Replacement of appropriate hormones may be required as the steroid dose is tapered.
- **Hyperthyroidism or Hypothyroidism:** Thyroid disorders can occur at any time during treatment. Monitor patients for changes in thyroid function (at the start of treatment, periodically during treatment, and as indicated based on clinical evaluation) and for clinical signs and symptoms of thyroid disorders.

- **Grade 2** hyperthyroidism events (and **Grade 2-4** hypothyroidism):
  - In hyperthyroidism, non-selective beta-blockers (e.g. propranolol) are suggested as initial therapy.
  - In hypothyroidism, thyroid hormone replacement therapy, with levothyroxine or liothyroinine, is indicated per standard of care.
- **Grade 3-4** hyperthyroidism
  - Treat with an initial dose of IV corticosteroid followed by oral corticosteroids. When symptoms improve to Grade 1 or less, steroid taper should be started and continued over no less than 4 weeks. Replacement of appropriate hormones may be required as the steroid dose is tapered.
- **Hepatic:**
  - For **Grade 2** events, monitor liver function tests more frequently until returned to baseline values (consider weekly).
    - Treat with IV or oral corticosteroids
  - For **Grade 3-4** events, treat with intravenous corticosteroids for 24 to 48 hours.
  - When symptoms improve to Grade 1 or less, a steroid taper should be started and continued over no less than 4 weeks.
- **Renal Failure or Nephritis:**
  - For **Grade 2** events, treat with corticosteroids.
  - For **Grade 3-4** events, treat with systemic corticosteroids.
  - When symptoms improve to Grade 1 or less, steroid taper should be started and continued over no less than 4 weeks.
- **Management of Infusion Reactions:** Signs and symptoms usually develop during or shortly after drug infusion and generally resolve completely within 24 hours of completion of infusion.

The table below shows treatment guidelines for subjects who experience an infusion reaction associated with administration of pembrolizumab.

**Table 5 Infusion Reaction Treatment Guidelines**

NCI CTCAE Grade	Treatment	Premedication at subsequent dosing
Grade 1 Mild reaction; infusion interruption not indicated; intervention not indicated	Increase monitoring of vital signs as medically indicated until the subject is deemed medically stable in the opinion of the investigator.	None
Grade 2 Requires infusion interruption but responds promptly to symptomatic treatment (e.g., antihistamines, NSAIDS, narcotics, IV fluids); prophylactic medications indicated for < =24 hrs	Stop Infusion and monitor symptoms. Additional appropriate medical therapy may include but is not limited to: IV fluids Antihistamines NSAIDS Acetaminophen Narcotics Increase monitoring of vital signs as medically indicated until the subject is deemed medically stable in the opinion of the investigator. If symptoms resolve within one hour of stopping drug infusion, the infusion may be restarted at 50% of the original infusion rate (e.g., from 100 mL/hr to 50 mL/hr). Otherwise dosing will be held until symptoms resolve and the subject should be premedicated for the next scheduled dose. Subjects who develop Grade 2 toxicity despite adequate premedication should be permanently discontinued from further trial treatment administration.	Subject may be premedicated 1.5h (± 30 minutes) prior to infusion of pembrolizumab (MK-3475) with:  Diphenhydramine 50 mg po (or equivalent dose of antihistamine).  Acetaminophen 500-1000 mg po (or equivalent dose of antipyretic).
Grades 3 or 4 Grade 3: Prolonged (i.e., not rapidly responsive to symptomatic medication and/or brief interruption of infusion); recurrence of symptoms following initial improvement; hospitalization indicated for other clinical sequelae (e.g., renal impairment, pulmonary infiltrates) Grade 4: Life-threatening; pressor or ventilatory support indicated	Stop Infusion. Additional appropriate medical therapy may include but is not limited to: IV fluids Antihistamines NSAIDS Acetaminophen Narcotics Oxygen Pressors Corticosteroids Epinephrine  Increase monitoring of vital signs as medically indicated until the subject is deemed medically stable in the opinion of the investigator. Hospitalization may be indicated. Subject is permanently discontinued from further trial treatment administration.	No subsequent dosing

Appropriate resuscitation equipment should be available in the room and a physician readily available during the period of drug administration.

## 5.5 Concomitant Medications/Vaccinations (allowed & prohibited)

Medications or vaccinations specifically prohibited in the exclusion criteria are not allowed during the ongoing trial. If there is a clinical indication for one of these or other medications or

vaccinations specifically prohibited during the trial, discontinuation from trial therapy or vaccination may be required. The investigator should discuss any questions regarding this with the Merck Clinical team. The final decision on any supportive therapy or vaccination rests with the investigator and/or the subject's primary physician.

### **5.5.1 Acceptable Concomitant Medications**

All treatments that the investigator considers necessary for a subject's welfare may be administered at the discretion of the investigator in keeping with the community standards of medical care. All concomitant medication will be recorded on the case report form (CRF) including all prescription, over-the-counter (OTC), herbal supplements, and IV medications and fluids. If changes occur during the trial period, documentation of drug dosage, frequency, route, and date may also be included on the CRF.

All concomitant medications received within 28 days before the first dose of trial treatment and 30 days after the last dose of trial treatment should be recorded. Concomitant medications administered after 30 days after the last dose of trial treatment should be recorded for SAEs and ECIs as defined in Section 7.2.

### **5.5.2 Prohibited Concomitant Medications**

Subjects are prohibited from receiving the following therapies during the Screening and Treatment Phase (including retreatment for post-complete response relapse) of this trial:

- Antineoplastic systemic chemotherapy or biological therapy
- Immunotherapy not specified in this protocol
- Chemotherapy not specified in this protocol
- Investigational agents other than pembrolizumab
- Radiation therapy
  - Note: Radiation therapy to a symptomatic solitary lesion or to the brain may be allowed at the investigator's discretion.

Live vaccines within 30 days prior to the first dose of trial treatment and while participating in the trial. Examples of live vaccines include, but are not limited to, the following: measles, mumps, rubella, varicella/zoster, yellow fever, rabies, BCG, and typhoid vaccine.

- Systemic glucocorticoids for any purpose other than to modulate symptoms from an event of clinical interest of suspected immunologic etiology. The use of physiologic doses of corticosteroids may be approved after consultation with the Sponsor.

Subjects who, in the assessment by the investigator, require the use of any of the aforementioned treatments for clinical management should be removed from the trial. Subjects may receive other medications that the investigator deems to be medically necessary. Daily or regular use of NSAIDs should be avoided except for the aspirin as specified in the trial. Concomitant NSAID use more frequently than once per week may be allowed at the investigator's discretion.

The Exclusion Criteria describes other medications which are prohibited in this trial.

There are no prohibited therapies for patients after they discontinue study treatment.

## 5.6 Diet/Activity/Other Considerations

### 5.6.1 Diet

Subjects should maintain a normal diet unless modifications are required to manage an AE such as diarrhea, nausea or vomiting.

### 5.6.2 Contraception

Pembrolizumab may have adverse effects on a fetus in utero. Furthermore, it is not known if pembrolizumab has transient adverse effects on the composition of sperm.

For this trial, male subjects will be considered to be of non-reproductive potential if they have azoospermia (whether due to having had a vasectomy or due to an underlying medical condition).

Female subjects will be considered of non-reproductive potential if they are either:

1. postmenopausal (defined as at least 12 months with no menses without an alternative medical cause; in women < 45 years of age a high follicle stimulating hormone (FSH) level in the postmenopausal range may be used to confirm a post-menopausal state in women not using hormonal contraception or hormonal replacement therapy. In the absence of 12 months of amenorrhea, a single FSH measurement is insufficient.);

OR

2. have had a hysterectomy and/or bilateral oophorectomy, bilateral salpingectomy or bilateral tubal ligation/occlusion, at least 6 weeks prior to screening;

OR

3. has a congenital or acquired condition that prevents childbearing.

Female and male subjects of reproductive potential must agree to avoid becoming pregnant or impregnating a partner, respectively, while receiving study drug and for 120 days after the last dose of study drug by complying with one of the following:

1. practice abstinence† from heterosexual activity;

OR

2. use (or have their partner use) acceptable contraception during heterosexual activity.

Acceptable methods of contraception are‡:

Single method (one of the following is acceptable):

- intrauterine device (IUD)
- vasectomy of a female subject's male partner
- contraceptive rod implanted into the skin

Combination method (requires use of two of the following):

- diaphragm with spermicide (cannot be used in conjunction with cervical cap/spermicide)
- cervical cap with spermicide (nulliparous women only)
- contraceptive sponge (nulliparous women only)
- male condom or female condom (cannot be used together)
- hormonal contraceptive: oral contraceptive pill (estrogen/progestin pill or progestin-only pill), contraceptive skin patch, vaginal contraceptive ring, or subcutaneous contraceptive injection

†Abstinence (relative to heterosexual activity) can be used as the sole method of contraception if it is consistently employed as the subject's preferred and usual lifestyle and if considered acceptable by local regulatory agencies and ERCs/IRBs. Periodic abstinence (e.g., calendar, ovulation, sympto-thermal, post-ovulation methods, etc.) and withdrawal are not acceptable methods of contraception.

‡If a contraceptive method listed above is restricted by local regulations/guidelines, then it does not qualify as an acceptable method of contraception for subjects participating at sites in this country/region.

Subjects should be informed that taking the study medication may involve unknown risks to the fetus (unborn baby) if pregnancy were to occur during the study. In order to participate in the study subjects of childbearing potential must adhere to the contraception requirement (described above) from the day of study medication initiation (or 14 days prior to the initiation of study medication for oral contraception) throughout the study period up to 120 days after the last dose of trial therapy. If there is any question that a subject of childbearing potential will not reliably comply with the requirements for contraception, that subject should not be entered into the study.

### **5.6.3 Use in Pregnancy**

If a subject inadvertently becomes pregnant while on treatment with pembrolizumab, the subject will immediately be removed from the study. The site will contact the subject at least monthly and document the subject's status until the pregnancy has been completed or terminated. The outcome of the pregnancy will be reported to the Sponsor and to Merck without delay and within 24 hours to the Sponsor and within 2 working days to Merck if the outcome is a serious adverse experience (e.g., death, abortion, congenital anomaly, or other disabling or life-threatening complication to the mother or newborn).

The study investigator will make every effort to obtain permission to follow the outcome of the pregnancy and report the condition of the fetus or newborn to the Sponsor. If a male subject impregnates his female partner the study personnel at the site must be informed immediately and the pregnancy reported to the Sponsor and to Merck and followed as described above and in Section 7.2.

### **5.6.4 Use in Nursing Women**

It is unknown whether pembrolizumab is excreted in human milk. Since many drugs are excreted in human milk, and because of the potential for serious adverse reactions in the nursing infant, subjects who are breast-feeding are not eligible for enrollment.

### 5.6.5 Subject Withdrawal/Discontinuation Criteria

Subjects may withdraw consent at any time for any reason or be dropped from the trial at the discretion of the investigator should any untoward effect occur. In addition, a subject may be withdrawn by the investigator or the Sponsor if enrollment into the trial is inappropriate, the trial plan is violated, or for administrative and/or other safety reasons. Specific details regarding discontinuation or withdrawal are provided in Section 6.3 - Other Procedures.

A subject must be discontinued from the trial for any of the following reasons:

- The subject or legal representative (such as a parent or legal guardian) withdraws consent.
- Confirmed radiographic disease progression

*Note:* For a clinically stable subject with first radiologic evidence of disease progression (e.g., unconfirmed), it is at the discretion of the site investigator to continue treating the subject

*Note:* A subject may be granted an exception to continue on treatment with confirmed radiographic progression if clinically stable or clinically improved.

- Unacceptable adverse experiences as described in Section 7.4
- Intercurrent illness that prevents further administration of treatment
- Investigator's decision to withdraw the subject
- The subject has a confirmed positive serum pregnancy test
- Noncompliance with trial treatment or procedure requirements
- The subject is lost to follow-up
- Administrative reasons

The End of Treatment and Follow-up visit procedures are listed in Section 6 (Protocol Flow Chart) and Section 6.3 - Other Procedures. After the end of treatment, each subject will be followed for 30 days for adverse event monitoring.

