### 3.3.1 Inclusion Criteria

1. Patients must have histologically confirmed melanoma that is metastatic or unresectable and for which standard curative or palliative measures do not exist or are no longer effective
2. Age >18 years
3. Eastern Cooperative Oncology Group (ECOG) performance status of 0 to 1.
4. Requirements for organ and marrow function:

Adequate bone marrow function:

leukocytes	≥ 3,000/mcL
absolute neutrophil count	≥ 1,500/mcL
platelets	≥ 100,000/mcL

Adequate hepatic function:

total bilirubin	within normal institutional limits
total bilirubin	≤ 1.5 X institutional upper limit
AST(SGOT)	≤ 2.5 X institutional upper limit of normal
ALT(SGPT)	≤ 2.5 X institutional upper limit of normal

Adequate renal function:

creatinine	≤ 1.5 X ULN
------------	-------------

5. Women of childbearing potential should have a negative urine or serum pregnancy within 72 hours prior to receiving the first dose of study drug. If the urine test is positive or cannot be confirmed as negative, a serum pregnancy test will be required.
6. Women of childbearing potential (Section 5.6.2) must be willing to use an adequate method of contraception, as outlined in Section 5.6.2 – Contraception, for the course of the study through 120 days after the last dose of study medication.

Note: Abstinence is acceptable if this is the usual lifestyle and preferred contraception for the subject.

7. Men of childbearing potential (Section 5.6.2) must agree to use an adequate method of contraception as outlined in Section 5.6.2- Contraception, starting with the first dose of study therapy through 120 days after the last dose of study therapy.

Note: Abstinence is acceptable if this is the usual lifestyle and preferred contraception for the subject.

8. Ability to understand a written informed consent document, and the willingness to sign it.

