### **3.4 Duration of Therapy**

In the absence of treatment delays due to adverse events, treatment may continue until:

- Disease progression
  - Note: For a clinically stable subject with first radiologic evidence of disease progression (e.g. unconfirmed), it is at the discretion of the primary investigator to continue treating the subject.
  - Note: A subject may be granted an exception, at the discretion of the primary investigator, to continue on treatment with confirmed radiographic progression if clinically stable or clinically improved.
- Inter-current illness that prevents further administration of treatment
- Unacceptable adverse event(s)
- Patients decides to withdraw from the study
- Significant patient non-compliance with protocol
- General or specific changes in the patients' condition render the patient unacceptable for further treatment in the judgment of the investigator.

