## 5 Treatment Plan

### 5.1 Dosage and Administration

**Table 1 Regimen Description**

Drug	Dose/Potency	Dose Frequency	Route of Administration	Regimen/Treatment Period	Use
Pembrolizumab	200 mg	Q3W	IV infusion	Day 1 of each 3 week cycle	Experimental
Ipilimumab	1 mg/kg	Q3wk X4	IV infusion	Day 1 of each 3 wk cycle, for 4 cycles	experimental
Aspirin	975 mg	PO BID	oral	Each day	experimental

Trial treatment should begin on the day of randomization or as close as possible to the date on which treatment is allocated/assigned.

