### **6.2.7 Tumor Imaging**

Prefer imaging of chest/abdomen and pelvis. PET/CT, CT, or MRI are acceptable. Imaging to be performed every 12 weeks (every 4 cycles).

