## Appendix 1 Schedule of Study Procedures and Assessments

Trial Period:	Screening Phase a	Treatment Cycles b								End of Treatment e	Post-Treatment Follow-up f
						To be repeated beyond 8 cycles					
Treatment Cycle/Title:	Main Study Screening	1	2	3	4	5	6	7	8	End of Treatment (EOT) visit	Safety Follow-up Visit
		-28 to -1	± 3	± 3	± 3	± 3	± 3	± 3	± 3		30 days post discon
Administrative Procedures											
Informed Consent	X										
Inclusion/Exclusion Criteria	X										
Demographics and Medical History	X										
Prior and Concomitant Medication Review	X										
Post-study anticancer therapy status										X	X
Survival Status										X	X
Trial Treatment Administration											
Ipilimumab		X	X	X	X						
Pembrolizumab		X	X	X	X	X	X	X	X		
Aspirin		X	X	X	X	X	X	X	X		
Clinical Procedures/Assessments											
Review Adverse Events		X	X	X	X	X	X	X	X		X
Full Physical Examination	X	X	X	X	X	X	X	X	X		X
Vital Signs and Weight	X	X	X	X	X	X	X	X	X		X
ECOG Performance Status	X	X	X	X	X	X	X	X	X		X
Laboratory Procedures/Assessments											
Pregnancy Test – Urine or Serum-HCG c	X										
PT/INR and aPTT	X										
CBC with Differential	X	X	X	X	X	X	X	X	X		
Comprehensive Serum Chemistry Panel	X	X	X	X	X	X	X	X	X		
Urinalysis	X										
T3, FT4 and TSH	X	X	X	X	X	X	X	X	X		
Tumor Tissue Collection g	X										
Efficacy Measurements											
Tumor Imaging d	X				X				X		

a. Screening procedures to be completed within 28 days of C1D1, except laboratory tests for screening should be performed within 10 days prior to the first dose of treatment.

- b. Patients will take aspirin daily and receive pembrolizumab and ipilimumab every 3 weeks for 4 cycles. After 4 cycles, ipilimumab will be discontinued and patients will continue receiving pembrolizumab every 3 weeks while taking aspirin daily.
- c. Women of childbearing potential: negative urine or serum pregnancy test within 72 hours prior to receiving trial treatment. If urine test is positive or non-confirmatory, a serum pregnancy test will be required.
- d. Prefer imaging of chest/abdomen and pelvis. PET/CT, CT, or MRI are acceptable.

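### Pregnancy requires removal from the trial, but Appendix 1 schedules no repeat pregnancy test after screening: 7 of the 8 displayed dosing visits, 3 of the 4 ipilimumab doses and all later cycles lack one

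*Combined protocol and SAP*

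**What the plan says.** **What must happen if a subject is pregnant.** Section 5.6.5 gives a list of reasons for which discontinuation is mandatory. One is "The subject has a confirmed positive serum pregnancy test". Section 5.6.3 says of a subject who becomes pregnant on pembrolizumab that "the subject will immediately be removed from the study".

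**When pregnancy is tested.** The pregnancy-test row of Appendix 1 has one mark, under screening. It has none under Cycles 1 to 8, end of treatment or safety follow-up. Its footnote c reads "Women of childbearing potential: negative urine or serum pregnancy test within 72 hours prior to receiving trial treatment". Inclusion criterion 5 (section 3.3.1) places the test "within 72 hours prior to receiving the first dose of study drug". Table 6 lists urine and serum pregnancy tests and says who has them, but not how often.

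**How long dosing lasts.** Table 1 gives ipilimumab on "Day 1 of each 3 wk cycle, for 4 cycles". Pembrolizumab and aspirin carry on. Section 3.4 says "In the absence of treatment delays due to adverse events, treatment may continue until" and then lists stopping events, none of which is a maximum number of cycles. Appendix 1 heads its later cycle columns "To be repeated beyond 8 cycles".

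**The concern.** One of the mandatory stops is triggered by a test result, yet after the baseline test nothing in the schedule would produce that result. A site that follows Appendix 1 exactly could keep dosing through an early pregnancy that occurs despite contraception, until the subject reports it or someone suspects it. Section 7.2 works the same way: it obliges investigators to report pregnancies that are spontaneously reported to them.

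The protocol itself states the hazard. Section 4.2.5 says ipilimumab can harm a fetus. It describes dose-related pregnancy loss and infant mortality in monkeys, and expects larger effects in the second and third trimesters, so early detection would allow dosing to stop before then. Section 5.6.2 says pembrolizumab may also affect a fetus. Section 5.6.3 plans expressly for inadvertent pregnancy on treatment, so the protocol does not assume that contraception always works.

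**Working it through.** The plan gives no figure to reproduce. The check is a comparison of passages and a count.

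**Step 1: is the single mark deliberate, or could Table 6 imply a test at every cycle?** Table 6 lists all the laboratory tests. Appendix 1 says when each is done:

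| Appendix 1 row | Screening | Cycles 1 to 8 |
|---|---|---|
| CBC; chemistry; T3, FT4 and TSH | marked | marked at all 8 |
| PT/INR and aPTT; urinalysis | marked | none |
| Pregnancy test | marked | none |

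Tests listed in Table 6 fall into both patterns, so being listed there does not create a test at each cycle. The text under Table 6 allows pre-dose laboratory work up to 72 hours before dosing after Cycle 1. That sets a window for scheduled tests and does not add tests.

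**Step 2: which doses does the screening test serve?** Inclusion criterion 5 fixes it to the 72 hours before the first dose, so it serves Cycle 1.

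**Step 3: count the doses with no repeat test.**
- Displayed dosing visits: 8 (Cycles 1 to 8). Served by the baseline test: 1. Without a repeat test: 8 − 1 = 7 (Cycles 2 to 8).
- Ipilimumab doses: 4 (Cycles 1 to 4). Served by the baseline test: 1. Without a repeat test: 4 − 1 = 3 (Cycles 2 to 4).
- Cycles after the eighth: the cycle procedures repeat, but the pregnancy row has no cycle mark to repeat, so none of these doses has a test.

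**Step 4: the same count with a test before every dose.** Visits without a test become 8 − 8 = 0, and ipilimumab doses without one become 4 − 4 = 0. The repeat instruction would then carry the test into later cycles.

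**The case against.** **Footnote c may already cover every dose.** It speaks of trial treatment, not the first dose, and section 5.2 uses that term for the Day 1 dosing of every cycle. Taken alone, the footnote could be read that way. But it is attached to a row marked only at screening, and inclusion criterion 5 says first dose, so screening-only is the better reading. The ambiguity is a further reason to reword the footnote.

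**The trial has other safeguards.** Contraception is required until 120 days after the last dose. Exclusion 10 bars anyone expecting to conceive. Section 5.6.2 bars anyone whose contraceptive compliance is in doubt. Appendix 1 has an examination and adverse-event review at each cycle, and section 6 allows unscheduled procedures. All of this stands and lowers the risk. These measures prevent pregnancy or react to suspicion of it; none is a scheduled check for it.

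**No frequency is prescribed.** This also stands. Nothing in the documents requires repeat testing, so its frequency is a design choice.

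**Stronger readings that the documents do not support.**
- A reader might infer that the sections contradict each other. They do not: the stopping rule still applies whenever any test is positive.
- A reader might infer that doses after Cycle 1 have no test before them at all. The baseline test precedes every dose; what is missing is a repeat.
- A reader might infer that the first on-treatment scan comes only after all four ipilimumab doses. Section 6.2.7 sets imaging every 12 weeks, but Appendix 1 marks it under Cycles 4 and 8, and section 5.2 puts procedures before dosing. The order is not settled, and imaging is not a pregnancy test in any case.
- For the same reason, no general claim can be made about testing at the imaging interval. Tests at Cycles 1 and 5 would leave 3 of 4 ipilimumab doses without one; tests at baseline and Cycles 4 and 8 would leave 2 of 4.

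**Conclusion.** The point holds as a patient-safety monitoring gap. No repeat pregnancy test is scheduled before 7 of the 8 displayed dosing visits, including 3 of the 4 ipilimumab doses, or before any later cycle, although pregnancy requires removal.

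The counts rest on two assumptions: that footnote c takes its timing from the row it annotates, and that the screening test serves the first dose only. The 8 is the number of cycles displayed, not a limit on treatment.

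These are counts of scheduled tests, not of expected pregnancies. The documents do not give the number of women of childbearing potential, so no risk can be estimated. The gap concerns that subgroup only. It has no bearing on the response rate, sample size or error rates. The change is worth making because the potential harm is serious, the protocol already requires the stop, and the remedy is cheap.

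**What to change.** In Appendix 1, mark the pregnancy-test row at each cycle, so that the repeat instruction carries it past Cycle 8. Reword footnote c along these lines:

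*For women of childbearing potential, a negative pregnancy test (urine or serum) is required no more than 72 hours before the first dose and before each later dose. If a urine result is positive, or cannot be confirmed as negative, a serum test is required before dosing.*

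The window matches the one section 6.2.5 already allows for pre-dose laboratory work after Cycle 1.

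The cost is one row and one footnote, and one urine or serum hCG per cycle for women of childbearing potential. The serum assay can use blood already drawn at each cycle, so no extra visit is needed. A dose may occasionally be held briefly while a serum result is confirmed.
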